## 7. SAMPLE SIZE DETERMINATION

It was determined that a sample size of 100 subjects per treatment group would detect a significant difference in proportion of PASI-75 and IGA responders from Baseline to Week 24 between each dose group of PPC-06 and placebo group, assuming a 15% response rate for the placebo group and 45% for PPC-06 at Week 24. To provide sufficient evidence of treatment effect, both PASI and IGA based response rate must reject at the same significance level. The hypothesis testing for the three dose groups will be conducted sequentially from high to low dose (600 mg BID, 400 mg BID and 400 mg QD); therefore, the 2-sided Type I error rate from a chi-squared test remains at the 0.05 level. Assuming 50% dropout rate, about 100 subjects per treatment arm will be randomized to get approximately 50 completers in each treatment arm. The total sample size of 400 subjects will yield at least 84% power for hypothesis testing of the co-primary endpoints of a difference in PASI-75 and IGA responders from Baseline to Week 24 between PPC-06 doses and placebo.

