## 8. ANALYSIS POPULATIONS

The following analysis sets/populations will be used in this trial:

- Safety population: include all subjects who receive at least one dose of IP. The safety population is the population used for all safety analyses.
- Full analysis set (FAS) – All randomized subjects who receive at least one dose of investigational product and have at least one post dose efficacy assessment. The FAS population will be the primary population for the efficacy analyses
- Per Protocol (PP) population: include subjects in the FAS population who complete the study without any major protocol violations that are considered likely to affect the efficacy analysis outcomes of the study. Major protocol violations will include but not be restricted to the following:
  - Failure to meet the inclusion/exclusion criteria that are considered likely to affect the efficacy analysis outcomes of the study
  - Randomization error

- Usage of any prohibited concomitant medications or procedures
- Failure to have Week 24 assessment within the allowable window for either of the co-primary endpoints
- Failure to be compliant with treatment regimen

Additional criteria may be added to determine PP population. The composition of the PP population will be determined and documented in blind reviews of the database conducted prior to unblinding the study database. Subjects who used rescue medications or who discontinued due to unsatisfactory therapeutic effect will be included in the PP population. These subjects will be considered as treatment failures (i.e., non-responder for both PASI-75 and IGA) for all time points after the initiation of rescue medications or subject discontinuation.

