The imputation of missing post-baseline BSA, PSSI final score, NAPSI, and NRS scores will be performed using a similar method as described for PASI. The imputation of missing post-baseline PP PGA scores will be performed using a similar method as described for IGA. A pre-specified seed number of 132138 will be used in all imputation procedures. No imputation will be done to the health-related quality of life endpoints or safety endpoints.

- **Observed cases (OC)**: No imputation will be performed, only observed values will be analyzed.
- **m-NRI (response endpoint only)**: Subjects who used rescue medications or discontinued due to unsatisfactory therapeutic effect are considered as treatment failures (i.e., non-responder) for all time points after the initiation of rescue medications or subject discontinuation. For example, if a subject discontinued due to lack of efficacy, all visits

after the last planned visits will be imputed to non-responders. If a subject used rescue medication during the study, all visits after the start of the rescue medication will be imputed to non-responders regardless if the subject had an assessment or not. Other subjects with missing data will be kept as missing (i.e., no imputation). Discontinuation due to unsatisfactory therapeutic effect will be identified by discontinuation reason = "Other" with a comment "lack of efficacy" on the eCRF.

- **LOCF:** The last observed value will be carried forward for any subsequent missing values. Baseline values will not be carried forward.

A summary of the imputation methods for all efficacy endpoints is shown below:

Endpoint	Analysis Population	Imputation Methods
PASI-75 at Week 24	FAS	MI, m-NRI, LOCF, OC
	PP	m-NRI
IGA score of clear or almost clear at Week 24	FAS	MI, m-NRI, LOCF, OC
	PP	m-NRI
Change from Baseline and percent change from Baseline in PASI Total Score by Visit	FAS	MI, LOCF, OC
	PP	OC
PASI-50 and PASI-75 by Visit	FAS	MI, m-NRI, LOCF, OC
	PP	m-NRI
IGA score of clear or almost clear by Visit	FAS	MI, m-NRI, LOCF, OC
	PP	m-NRI
Change from Baseline and percent change from Baseline in BSA by Visit	FAS	MI, LOCF, OC
	PP	OC
Change from Baseline in NPSI by Visit	FAS	MI, LOCF, OC
	PP	OC
Change from Baseline in PSSI by Visit	FAS	MI, LOCF, OC
	PP	OC
Change from Baseline in PP PGA by Visit	FAS	MI, LOCF, OC
	PP	OC
Change from Baseline in NRS by Visit	FAS	MI, LOCF, OC
	PP	OC
Time to PASI-75	FAS	OC
Time to achieving an IGA score of clear or almost clear	FAS	OC
QIDS-SR 16	FAS	OC

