### **12.7.2 Secondary Efficacy Endpoints**

The secondary endpoints are the following:

- Change from Baseline and percent change from Baseline in total PASI Score by Visit in the Double-Blind Treatment Period
- Proportion of subjects who achieve PASI-50 and PASI-75 at each visit in the Double-Blind Treatment Period
- Proportion of subjects who achieve an IGA score of clear or almost clear at each visit in the Double-Blind Treatment Period
- Change from Baseline and percent change from Baseline in percent of affected BSA at each visit in the Double-Blind Treatment Period
- For applicable subjects present with non-zero baseline NAPSI score (score range 0-8) in target nail, change from baseline in Nail Psoriasis Severity Index (NAPSI) of the target fingernail at Weeks 12, 16 and 24
  - All fingernails will be scored at Baseline and the target nail will be selected as the one with the worst (highest) score by investigator; Only the target nail will be evaluated in the subsequent visits.
  - If a target nail was not identified on the CRF, for purpose of analysis, it will be selected programmatically as the fingernail with the worst score at Baseline. If more than 1 nail has the same worst score, then the target nail will be the first nail according to the order of digit collected on the CRF (i.e., digit 1/thumb, digit 2...digit 5). If the same digit from both hands have the same worst score, the target nail will be selected from the left hand.
  - If score is 0 at Baseline, then the respective assessments at future visits would not be required.
- For applicable subjects present with non-zero baseline score, change from baseline by visit in Psoriasis Scalp Score Index (PSSI, score range 0-72) and Palmoplantar Psoriasis Physician's Global Assessment (PP PGA, score range 0-4) in the Double-Blind Treatment Period;
  - If score is 0 for PSSI and PP PGA at Baseline, then the respective assessments at future visits would not be required;
- Change from Baseline and percent change from Baseline in pruritus Numeric rating scale (NRS) score (score range 0-10) at each visit in the Double-Blind Treatment Period
- Time to achieving a PASI-75 response, defined as time in days from baseline to first achieving a reduction of 75% or greater from Baseline in PASI. Subjects who did not achieve PASI-75 by the last assessment or withdrew prior to the last study visit will be censored at their last PASI assessment

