- Time to achieving an IGA score of clear or almost clear, defined as time in days from baseline to first achieving an IGA score of 0 or 1. Subjects who did not achieve an IGA of 0 or 1 at the last assessment or withdrew prior to the last study visit will be censored at their last IGA assessment

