### **12.8.2 Secondary Efficacy Analyses**

All secondary efficacy analyses will be performed on the FAS and PP populations.

The following categorical secondary efficacy endpoints will be summarized using the number and percentage of subjects within each category for each treatment group. A same logistic regression model as used for the primary endpoint will be performed. Each PPC-06 group will be compared to placebo separately as described in the primary analysis.

- Proportion of subjects who achieve PASI-50 and PASI-75 by visit in the Double-Blind Treatment Period
- Proportion of subjects who achieve an IGA score of clear or almost clear by visit in the Double-Blind Treatment Period

The observed values and change from baseline in PP PGA will be summarized as categorical endpoint using frequency counts and percentages. The change from baseline in severity categories will be compared between treatment groups using a Wilcoxon rank sum test.

The following continuous secondary efficacy endpoints will be summarized descriptively and analyzed using an Analysis of Covariance (ANCOVA) including factors for treatment, baseline

BMI, and pooled analysis center. Each PPC-06 group will be compared to placebo separately. The least square mean (LSM) difference, along with the 95% CI and p-value will be reported.

- Change from Baseline and percent change from Baseline in total PASI Score by visit in the Double-Blind Treatment Period
- Change from Baseline and percent change from Baseline in percent of affected BSA by Visit in the Double-Blind Treatment Period
- For applicable subjects, change from baseline in NAPSI of the target fingernail at Weeks 12, 16 and 24
- For applicable subjects, change from baseline by visit in PSSI in the Double-Blind Treatment Period
- Change from Baseline and percent change from Baseline in pruritus NRS score by Visit in the Double-Blind Treatment Period

The following time to event variables will be analyzed using the Kaplan-Meier (KM) method. Subjects who have not achieved treatment response by the last visit or discontinue the study will be censored at their last visit. The mean, 25th, 50th, and 75th percentile time to achieving a treatment success will be reported; log-rank test will be performed for the comparison between each PPC-06 arm and placebo.

- Time to achieving PASI-75 response
- Time to achieving IGA 0 or 1

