14.2.2.9.4.1	Analysis of Secondary Efficacy Outcome: Change from Baseline in Pruritus Numeric Rating Scale (NRS) Score by Visit, Double-Blind Treatment Period, PP Population, OC
14.2.2.9.4.2	Analysis of Secondary Efficacy Outcome: Percent Change from Baseline in Pruritus Numeric Rating Scale (NRS) Score by Visit, Double-Blind Treatment Period, PP Population, OC
14.2.2.10	Analysis of Secondary Efficacy Outcome, Time to Achieving PASI-75 Response, Full Analysis Set, OC
14.2.2.11	Analysis of Secondary Efficacy Outcome, Time to Achieving IGA Score of Clear or Almost Clear, Full Analysis Set, OC
14.2.3	Summary of Quality of Life (QoL) Tables
14.2.3.1	Analysis of Quality of Life Outcome: Change from Baseline in QIDS-SR16 Total Score by Visit, Full Analysis Set, OC
14.2.3.2.1	Analysis of Quality of Life Outcome: Change from Baseline in DLQI Total Score by Visit, Full Analysis Set, OC
14.2.3.2.2	Analysis of Quality of Life Outcome: Change from Baseline in DLQI Individual Domains by Visit, Full Analysis Set, OC
14.2.3.3.1	Analysis of Quality of Life Outcome: Change from Baseline in SF-12 Subdomains by Visit, Full Analysis Set, OC

14.2.3.3.2	Analysis of Quality of Life Outcome: Change from Baseline in SF-12 Summary Scores by Visit, Full Analysis Set, OC
14.2.3.4	Analysis of Quality of Life Outcome: Change from Baseline in WPAI: PSO Score by Visit, Full Analysis Set, OC
14.2.3.5	Analysis of Quality of Life Outcome: Summary of HEOR Score by Visit, Full Analysis Set, OC
14.3	Summary of Safety Tables
14.3.1.1.1	Overall Summary of Adverse Events by Treatment, Titration Period, Safety Population
14.3.1.1.2	Overall Summary of Adverse Events by Treatment, Treatment Period, Safety Population
14.3.1.1.3	Overall Summary of Adverse Events by Treatment, Overall, Safety Population
14.3.1.2	Summary of Treatment-emergent Adverse Events by System Organ Class and Preferred Term in Descending Frequency, Safety Population
14.3.1.3	Summary of Treatment-emergent Adverse Events by System Organ Class, Preferred Term, and Maximum Severity, Safety Population
14.3.1.4	Summary of Treatment-emergent Adverse Events by System Organ Class, Preferred Term, and Maximum Causality, Safety Population
14.3.2.1	Summary of Clinical Laboratory Results by Treatment and Visit, Chemistry, Safety Population
14.3.2.2	Summary of Clinical Laboratory Results by Treatment and Visit, Hematology, Safety Population

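### Time to PASI-75 and time to IGA 0/1 censor every discontinuation whatever its reason, so active-arm response percentiles are biased early against the SAP's own m-NRI and per-protocol failure rule

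*SAP*

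**What the plan says.** SAP 12.8.2 analyses both endpoints by Kaplan-Meier, with percentiles of time to response and a log-rank test of each PPC-06 arm against placebo. Its censoring rule is: "Subjects who have not achieved treatment response by the last visit or discontinue the study will be censored at their last visit". The endpoint definitions in SAP 12.7.2 agree in substance. For PASI-75, a subject who "withdrew prior to the last study visit will be censored at their last PASI assessment"; for IGA, one who "withdrew prior to the last study visit will be censored at their last IGA assessment". None of these sentences distinguishes reasons for leaving.

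The only data handling planned is observed cases in the FAS. This is stated in the imputation summary in SAP 9 and in the table list, for example "Analysis of Secondary Efficacy Outcome, Time to Achieving PASI-75 Response, Full Analysis Set, OC". No sensitivity version is listed for either endpoint.

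Elsewhere the SAP treats some of the same subjects differently. The m-NRI rule in SAP 9 reads: "Subjects who used rescue medications or discontinued due to unsatisfactory therapeutic effect are considered as treatment failures (i.e., non-responder) for all time points after" rescue starts or the subject leaves. SAP 8, on the per-protocol population, says of the same two groups: "These subjects will be considered as treatment failures (i.e., non-responder for both PASI-75 and IGA) for all time points" from that moment. Protocol 6.7 also calls a subject who needs rescue a treatment failure, while allowing continued follow-up for safety.

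The primary method does not follow this rule. Under SAP 9 and Protocol 8.7.3, multiple imputation covers rescue users and lack-of-efficacy leavers like anyone else with missing data.

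**The concern.** Censoring is harmless to a Kaplan-Meier estimate when those censored would have responded at the same rate as those who remain. Someone who leaves because the drug is not working is a poor candidate for that assumption. Under the m-NRI and per-protocol rules such a subject can no longer respond at all, which makes the departure a competing failure event. Taking these subjects out of the risk set without counting a failure raises one minus Kaplan-Meier and pulls its percentiles earlier.

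Rescue users raise a related problem. They may stay in the study, and under observed cases a PASI-75 or IGA 0/1 reached after rescue counts as a response, where m-NRI scores a failure.

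At stake are the percentiles in Tables 14.2.2.10 and 14.2.2.11 and how they sit beside the m-NRI response rates for the same outcome. The issue could matter in this trial because heavy dropout is planned: "Assuming 50% dropout rate, about 100 subjects per treatment arm will be randomized to get approximately 50 completers".

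**Working it through.** **1. The plan's own figure.** No power or event count is stated for the time-to-response endpoints. SAP 7 gives at least 84% power for the co-primaries with 15% against 45%, about 50 completers per arm and two-sided 0.05.
- Null SE = √(2 × 0.30 × 0.70/50) = 0.0917.
- Alternative SE = √((0.15 × 0.85 + 0.45 × 0.55)/50) = 0.0866.
- Power = Φ((0.30 − 1.96 × 0.0917)/0.0866) = Φ(1.39) = 0.918 per endpoint.
- For two endpoints taken as independent, 0.918² = 0.842.

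The figure reproduces. It supplies only the response rates and the dropout used below.

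**2. Assumptions.**
- From the SAP: 100 per arm, and 15% (placebo) and 45% (active) responding.
- Assumed: responders spread evenly over Weeks 8, 12, 16, 20 and 24; L lack-of-efficacy leavers spread evenly after Weeks 8, 12, 16 and 20; no other dropout. L is not in the documents, so a range is shown.

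**3. Planned method.** One minus Kaplan-Meier is 1 − Π(1 − d/n). For the active arm with L = 20, nine respond at each visit and five leave after each of the first four:

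1 − (91/100)(77/86)(63/72)(49/58)(35/44) = 52.1%.

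**4. Same subjects under the failure rule.** The Aalen-Johansen estimate sums S(t−) × d/n, where S is the probability of having neither responded nor left:

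1.00 × 9/100 + 0.86 × 9/86 + 0.72 × 9/72 + 0.58 × 9/58 + 0.44 × 9/44 = 45.0%.

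**5. Week 24 response, by number of leavers.**

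| Arm | Failure rule | Leavers censored, as planned |
|---|---|---|
| Placebo | 15.0% | 15.9% (L = 10), 16.9% (20), 18.2% (30), 19.9% (40) |
| Active | 45.0% | 46.5% (L = 5), 48.1% (10), 52.1% (20), 57.5% (30) |

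A simulation of 3,000 trials added other dropout to bring the total to 50%. Lack-of-efficacy dropout occurred only in subjects who would not respond. With 20, 40 or 60% of dropouts due to lack of efficacy, placebo was 16.1, 17.2 or 18.8% and active 48.7, 52.9 or 58.6%. The pattern is the same.

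**6. Percentiles, which are what the tables report.**
- Active median: not reached at 45.0%. With L = 16, (91/100)(78/87)(65/74)(52/61)(39/48) = 0.496, so 50.4% is printed and the median falls at Week 24.
- Active 25th percentile: Week 16 either way at L = 20 (27.0% against 28.7%). It can move when the curve passes close to 25% at a visit. If 30 of 100 respond (an assumed lower rate) and L = 20, then 1 − (94/100)(83/89)(72/78)(61/67) = 26.3% at Week 20. The failure rule gives 24% at Week 20 and 30% at Week 24, so the percentile moves from Week 24 to Week 20.
- Placebo: below 25% in every row above, so no percentile is reached under either handling.

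**7. Contrast with placebo.** With leavers kept as non-responders, the difference is 30.0 points. The log-rank observed-minus-expected is 17.2 with variance 13.9, so z = 17.2/√13.9 = 4.61. With leavers censored:

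| Leavers, placebo/active | Difference (points) | z |
|---|---|---|
| 20/20 | 35.2 | 4.80 |
| 30/10 | 29.9 | 4.15 |
| 40/5 | 26.6 | 3.68 |
| 10/30 | 41.7 | 5.51 |

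**The case against.** **The failure rule is not the primary rule.** A reader might infer that the time-to-response analysis contradicts the SAP's main analysis. It does not: multiple imputation also lets a lack-of-efficacy leaver be imputed as a responder. Whether the estimate is too high depends on the outcome one wants described, and a hypothetical reading in which leavers behave like stayers is coherent. This stands, so the conflict is stated here only against m-NRI and the per-protocol text. Multiple imputation does condition on each subject's earlier scores, so a poor course pulls the imputed value down. Kaplan-Meier uses only arm and time at risk, so it matches neither approach.

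**The size is assumed and may be small.** Protocol 5.4 lists no lack-of-efficacy reason. SAP 9 finds these subjects through the reason 'Other' plus a comment, which may yield few. This stands.

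**Little of it reaches the tables.** The shells print percentiles and log-rank p-values, and no Kaplan-Meier figure is listed. Placebo percentiles are not reached at the planned rate. This stands too, and confines the visible effect mainly to the active-arm 25th percentile and median.

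**The stakes are modest.** These are two of many secondary endpoints tested at an unadjusted 0.05, and response by visit is already analysed under m-NRI.

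The objections narrow the point without removing it. Nothing in the plan shows how the two endpoints look when acknowledged treatment failures are counted as failures.

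**Conclusion.** The point holds, with limits. Both endpoints censor all discontinuations alike. Against the m-NRI and per-protocol rules, that biases Kaplan-Meier response upward and its percentiles earlier whenever such a leaver is removed before a later response in the same arm. On the even-timing assumption with the plan's rates, the Week 24 excess is about 1 to 5 points for placebo (10 to 40 leavers) and 1.5 to 12.5 points for active (5 to 30 leavers). An active median first appears at about 16 leavers. The actual number of leavers is unknown.

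Two stronger readings are tempting and not supported. One is that the comparison is biased in a known direction: z falls if placebo loses more subjects for lack of efficacy and rises if the active arm does, and the documents do not say which to expect. The log-rank test also remains a legitimate comparison of cause-specific response hazards. The other is that the trial's main conclusion is exposed: the co-primary tests do not use this censoring. This is a secondary-endpoint matter worth correcting because the remedy is cheap.

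**What to change.** In SAP 12.7.2 and 12.8.2, the SAP 9 summary and the footnotes of Tables 14.2.2.10 and 14.2.2.11:

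- For a subject with no prior response, treat discontinuation for unsatisfactory effect or the start of rescue medication as a competing event. Censor at the last assessment only for other reasons.
- Report by arm the Aalen-Johansen cumulative incidence of response at Week 24 and the times at which it reaches 25, 50 and 75%, or not reached.
- Keep the log-rank test, described as comparing cause-specific hazards. Gray's test is optional.
- Keep the current Kaplan-Meier analysis as a sensitivity run.
- State that a response before discontinuation counts as an event. The 12.8.2 sentence, read literally, could censor it, although the endpoint is defined by first response.
- Reconcile last visit with last assessment as the censoring date. Also reconcile the FAS-only entry in SAP 9 with the opening of 12.8.2, which sends all secondary analyses to FAS and PP.

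Holding leavers in the risk set to Day 168 is not an equivalent shortcut once other dropouts are censored. The leavers keep full weight while others drop away, and the estimate runs low. A large-sample run with true rates of 15% and 45% gave about 14.7% and 43.9% that way, against 15.0% and 45.0% by Aalen-Johansen.

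The flags are already required for m-NRI. The cost is SAP wording and one extra programme run, and reported response will be slightly lower.

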### **12.8.3 Health-related Quality of Life Analyses**

All QoL endpoints will be summarized by visit and treatment group using descriptive statistics on the FAS population.

### **12.8.4 Subgroup Analyses**

The co-primary efficacy endpoints will be analyzed for the following subgroups:

- Baseline hsCRP (< 5 mg/L, >=5 mg/L)
- Baseline BMI (<30, >=30)
- Occurrence of diarrhea (Subjects reported diarrhea as adverse event by Week 24, subject did not report diarrhea by Week 24)

The same method as described in [Section 12.8.1](#) will be used for the subgroup analyses, except that no formal hypothesis testing will be performed.

